### **3.8.6. Pharmacokinetic Analyses**

Tovorafenib plasma concentrations at specified time points will be analysed using a validated bioanalytical method. All plasma concentrations of tovorafenib will be listed and summarized by nominal sample time using standard summary statistics for PK concentrations (geometric mean, geometric coefficient of variation, geometric standard deviation, arithmetic mean, standard deviation, minimum, maximum and n).

## 4. DEVIATIONS FROM PROTOCOL

Definition of efficacy analysis sets, Section [3.2.1](#).

## 6. APPENDIX

### 6.1. Best Overall Assessment by RECIST 1.1

Overall Response First Time Point	Overall Response Subsequent Time Point	Best Confirmed Overall Response
CR	CR	CR
CR	PR	PR a , SD, PD
CR	SD	SD provided minimum criteria for SD duration met, otherwise, PD
CR	PD	SD provided minimum criteria for SD duration met, otherwise, PD
CR	NE	SD provided minimum criteria for SD duration met, otherwise, NE
PR	CR	PR
PR	PR	PR
PR	SD	SD
PR	PD	SD provided minimum criteria for SD duration met, otherwise, PD
PR	NE	SD provided minimum criteria for SD duration met, otherwise, NE
NE	NE	NE

Abbreviations: Abbreviations: CR, complete response; NE, not all evaluated; PD, progressive disease; PR, partial response; SD, stable disease.

a If a CR is truly met at first time point, then any disease seen at a subsequent time point, even disease meeting PR criteria relative to baseline, makes the disease PD at that point (since disease must have reappeared after CR). Best response would depend on whether minimum duration of 8 weeks for SD was met. However, sometimes 'CR' may be claimed when subsequent scans suggest small lesions were likely still present and in fact the patient had PR, not CR at the first time point. Under these circumstances, the original CR should be changed to PR and the best response is PR.

## 6.2. RANO Response Criteria Incorporating MRI and Clinical Factor

RESPONSE CATEGORY	CRITERIA
Complete Response	

• Disappearance of all measurable and non-measurable enhancing disease

• Stable or improved nonenhancing FLAIR/T2 lesions

• No new lesions

• Clinically stable or improved with no reliance on corticosteroids (except for physiological replacement)

Partial Response	

• <math>\geq 50\%</math> decrease from baseline of all measurable enhancing lesions

• No progression of non-measurable disease

• Stable or improved nonenhancing FLAIR/T2 lesions

• No new lesions

• Clinically stable or improved, with stable or reduced corticosteroids compared to baseline

Progressive Disease	

• <math>\geq 25\%</math> increase from baseline in enhancing lesions despite stable or increasing steroid dose

• Significant increase in nonenhancing FLAIR/T2 lesions not attributable to other non-tumor causes

• Any new lesions

• Clinical deterioration not attributable to other non-tumor causes and not due to steroid decrease

Stable Disease	

• Does not meet other criteria for response or progression

• Stable nonenhancing FLAIR/T2 lesions

• Clinically stable with stable or reduced corticosteroids compared to baseline

Abbreviations: FLAIR/T2, T2-weighted fluid-attenuated inversion recovery; MRI, magnetic resonance imaging; RANO, Response Assessment in Neuro-Oncology.

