7.3.1. Efficacy Analyses

The efficacy analyses will be performed on the full analysis set (FAS) population which includes all patients who received at least 1 dose of study drug and have measurable disease as determined by the Investigator at baseline and have at least 1 follow-up imaging or radiographically confirmed progressive disease prior to the first imaging timepoint.

ORR as assessed by the proportion of patients with the best overall confirmed response of CR or PR, according to the appropriate tumor response criteria as assessed by Investigator will be calculated and an exact CI will be calculated. DOR in patients with best overall response of CR or PR as determined by the treating Investigator defined as from time of first tumor response to progression or date of data analysis, whichever occurs earlier will be calculated. PFS is defined as the time from the date of the first dose of study drugs to the first occurrence of disease progression according to the appropriate tumor response criteria as

assessed by Investigator, or death from any cause, whichever occurs earlier. OS is defined as the period from the date of the first dose of study drugs until the date of death from any cause. Kaplan-Meier curves will be plotted for DOR, PFS, and OS. TTR in patients with best overall response of CR or PR will be determined by the treating Investigator from the initiation of study treatment to the date of first response. The timepoint for the analysis of response for Phase 2 studies' primary efficacy objective will be when all patients have a minimum of 6 months of follow-up.

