- Complete Response (CR): Disappearance of all target lesions. Any pathological lymph nodes (whether target or non-target) must have reduction in short axis to <10 mm.
- PR: At least a 30% decrease in the sum of diameters of target lesions, taking as reference the baseline sum diameters.
- Progressive Disease (PD): At least a 20% increase in the sum of diameters of target lesions, taking as reference the smallest sum on study (this includes the baseline sum if that is the smallest on study). In addition to the relative increase of 20%, the sum must also demonstrate an absolute increase of at least 5 mm. (Note: the appearance of one or more new lesions is also considered progression).
- Stable Disease (SD): Neither sufficient shrinkage to qualify for PR nor sufficient increase to qualify for PD, taking as reference the smallest sum diameters while on study.

Evaluation of Non-Target Lesions

While some non-target lesions may actually be measurable, they need not be measured and instead should be assessed only qualitatively at the time points specified in the protocol.

- Complete Response (CR): Disappearance of all non-target lesions and normalization of tumor marker level. All lymph nodes must be non-pathological in size (<10 mm short axis).
- Non-CR/Non-PD: Persistence of one or more non-target lesion(s) and/or maintenance of tumor marker level above the normal limits.
- Progressive Disease (PD): Unequivocal progression (see comments below) of existing non-target lesions. (Note: the appearance of one or more new lesions is also considered progression).

Evaluation of Best Overall Response

The best overall response is determined once all the data for the patient is known. Guidance on the determination of tumor response at each time point is provided in Table 12. Complete or partial responses may be claimed only if the criteria for each are met at a subsequent time point as specified in the protocol (generally 4 weeks later). Guidance on the determination of best overall confirmed response is provided in Table 13.

Patients with a global deterioration of health status requiring discontinuation of treatment without objective evidence of disease progression at that time should be classified as having symptomatic deterioration. Every effort should be made to document objective disease progression, even after discontinuation of treatment.

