##### **3.1.3. Baseline Value and Change from Baseline**

Baseline value will be defined as the most recent non-missing value obtained prior to administration of first dose of study treatment. Change from baseline will be calculated by subtracting the baseline value from the relevant post-baseline assessment for each patient (i.e., post-baseline – baseline).

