### **3.2.4. Subgroup Analyses**

Due to the small sample size, subgroup analyses of key efficacy endpoints will only be performed for the following baseline variables:

- Sex (Female, Male)
- CNS tumor (Yes, No; tissue agnostic cohort)

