#### **3.3.2. Secondary Efficacy Variables**

##### **3.3.2.1. Duration of Response**

Duration of response (DOR) is defined as the interval from the date of the first documentation of tumor response (CR or PR) that was subsequently confirmed by investigator assessment to the date of first occurrence of radiographic disease progression based on RECIST 1.1 or RANO criteria or death due to any cause, whichever occurs earlier. If a patient does not experience progression or death by the data cutoff date, then the patient will be censored at the date of the last evaluable tumor assessment.

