### **3.7. Efficacy Analysis**

Each analysis of clinical efficacy endpoints will be performed with the efficacy analysis set, unless specified otherwise. All efficacy analyses will be presented by cohort, unless specified otherwise.

Efficacy analysis variables are defined in Section 3.3.

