### **3.7.2. Progression-Free Survival**

PFS is defined as the interval from the date of the first dose to radiographic disease progression based on RECIST 1.1 or RANO criteria or death by any cause, whichever occurs first. Details regarding censoring are included in Appendix 6.3.

Disease progressions reported during the long-term follow up period will be included in the derivation of PFS. The number and percentage of patients who experienced event and censoring will be presented with the corresponding reason as listed in Appendix 6.3. Summary statistics (25th percentile, median, 75th percentile, and the corresponding 95% CIs) will be presented for PFS time using the Kaplan-Meier method.

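### RANO enhancing-lesion progression is measured from pre-dose baseline, so DOR and PFS can run long in RANO-assessed patients whose tumours shrank; a nadir-referenced sensitivity analysis would show whether it matters

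*SAP*

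**What the plan says.** SAP 6.2, which repeats Table 14 in Protocol Appendix C, lists among the RANO progression criteria a 25% or greater "increase from baseline in enhancing lesions despite stable or increasing steroid dose". SAP 3.1.3 fixes that reference in time: "Baseline value will be defined as the most recent non-missing value obtained prior to administration of first dose of study treatment". The partial-response row of the same table is a fall of at least 50% from the same baseline.

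RECIST is handled differently. Protocol Appendix B requires a rise of at least 20% and at least 5 mm, "taking as reference the smallest sum on study (this includes the baseline sum if that is the smallest on study").

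The two criteria feed the same endpoints. SAP 3.3.2.1 ends DOR at the "first occurrence of radiographic disease progression based on RECIST 1.1 or RANO criteria or death due to any cause", and SAP 3.3.2.3 ends PFS in the same way. SAP 3.7.1 and 3.7.2 repeat this; in 3.7.2, PFS runs to "radiographic disease progression based on RECIST 1.1 or RANO criteria or death by any cause, whichever occurs first". SAP 3.7 adds: "All efficacy analyses will be presented by cohort, unless specified otherwise". RANO- and RECIST-assessed patients can therefore share one tissue-agnostic estimate. For PFS, Protocol 7.3.1 takes progression as "assessed by Investigator, or death from any cause, whichever occurs earlier".

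Neither document gives a nadir reference for RANO, explains the difference from RECIST, or plans an analysis of its effect.

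**The concern.** Under RECIST, a tumour that shrinks and regrows is called progressive on the way back up. Under the RANO line as written, the enhancing sum must first regain everything it lost and then exceed baseline by a quarter. A RANO responder can therefore lose the whole response and still be progression-free on this criterion.

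The direction is fixed. For a given patient, a threshold set from baseline is never reached before one set from the nadir, because the nadir includes baseline. The wording can delay progression on this criterion but cannot bring it forward.

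What is at stake is the reading of DOR and PFS in the tissue-agnostic cohort. SAP 6.3 can add to the effect: a patient who regrows well above the nadir but stays under the baseline threshold, meets no other progression criterion and changes therapy is censored and not counted as an event.

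**Working it through.** The documents give no figure of their own to reproduce here. SAP Table 1 is redacted and does not bear on the point. The check is threshold arithmetic.

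**Inputs**
- RANO progression: at least 25% above the reference; the reference is baseline (SAP 6.2, SAP 3.1.3).
- RANO partial response: at least 50% below baseline (SAP 6.2).
- RANO measure: sum of bidimensional products (Protocol Appendix C).
- RECIST progression: at least 20% and 5 mm above the smallest sum (Protocol Appendix B).
- Confirmation of response: at least 4 weeks later (SAP 3.3.1.1).

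**Assumption.** There is a single lesion, or all lesions change in proportion.

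**Formulas.** Let r = nadir / baseline.
- As written, progression is at 1.25 × baseline = (1.25 / r) × nadir.
- Nadir-referenced, progression is at 1.25 × nadir = 125r % of baseline.
- The gap in tumour doublings is log2[(1.25 / r) / 1.25] = log2(1 / r).

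| r | As written, × nadir | Nadir-referenced, × nadir | Nadir-referenced, % of baseline | Gap, doublings |
|---|---|---|---|---|
| 1.00 | 1.25 | 1.25 | 125 | 0 |
| 0.75 (stable disease) | 1.67 | 1.25 | 93.75 | 0.42 |
| 0.51 (stable disease) | 2.45 | 1.25 | 63.75 | 0.97 |
| 0.50 (minimum PR) | 2.50 | 1.25 | 62.5 | 1.00 |
| 0.25 | 5.00 | 1.25 | 31.25 | 2.00 |

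As written, the threshold is 125% of baseline in every row. The gap is not confined to responders: in stable disease it approaches one doubling as r nears 0.5.

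**RECIST for comparison.** With a baseline sum of 100 mm and a nadir of 70 mm (minimum PR), progression is at max(1.20 × 70, 70 + 5) = 84 mm, still below baseline.

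**Effect on confirmed response.** Suppose the RANO sum is 40% of baseline at one scan and 50% at the next, at least 4 weeks later. Against baseline, the second scan is still a 50% fall and can confirm the PR. Against the nadir, 50 / 40 = 1.25, which is progression. In general this can happen when 1.25r ≤ 0.50, that is r ≤ 0.40. Changing the reference can therefore move ORR and the set of patients evaluable for DOR.

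**Measurement error.** A 25% rise in a product is reached when both diameters grow by √1.25 = 1.118. On a 10 mm lesion that is 11.18 − 10, about 1.2 mm. If only one diameter grows, it takes 10 × 0.25 = 2.5 mm.

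**The case against.** The strongest reply is that this is a preference. Protocol and SAP agree with each other, baseline is defined, and RECIST uses a different measure for different tumours. That stands as far as it goes. A reader might infer an internal contradiction, or that the table misstates the RANO source it cites. The documents support neither: the criteria are not applied to the same tumours, and the source is not available here.

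A second reply is that this line may not date any event. Progression is investigator-assessed, SAP 3.3.1.1 introduces 6.2 as guidance for best response, and Protocol 6.19.1 places assessment under the Imaging Manual. Neither that manual nor the sub-protocol is available, so the reference sites used is unknown. This also stands, and limits the claim to what follows if the rule was applied as written.

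Third, other things can come first: a new lesion, a FLAIR/T2 increase, death or censoring. Clinical deterioration is on the RANO list, but DOR and PFS require radiographic progression, so whether it counts is unclear. With several lesions, Appendix C lets the enlarging ones be evaluated, so 2.5 times nadir is not a floor in that case.

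Fourth, the consequence may be small. The study ended early, follow-up may be as short as about 6 months (SAP 2.2.1), and DOR and PFS are secondary and descriptive. A reader might convert doublings into months of inflated DOR. That needs a growth rate the documents do not give, and the number of RANO-assessed patients is not given either.

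Finally, SAP 3.2.4 already plans a CNS-tumour subgroup for key efficacy endpoints. It may separate most RANO from RECIST patients, but it would compare them under different progression references and would not show what the reference does.

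**Conclusion.** The point holds as a modest, one-directional analysis issue. If SAP 6.2 was applied as written, enhancing-lesion progression in a RANO-assessed patient whose tumour shrank is called log2(1 / r) doublings later than under a nadir reference: none without shrinkage, close to one in stable disease near half of baseline, one at the minimum PR, and two at a nadir of 25%. These figures assume a single lesion or uniform change. DOR and PFS for such patients can be lengthened and cannot be shortened by this choice.

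The size in months and the effect on the cohort estimate cannot be established. It would go too far to say that the reported durations are biased by a known amount, or that the protocol criteria or any treatment rule should change.

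**What to change.** Change the SAP only. Keep investigator-assessed DOR and PFS as the main analysis and add one sensitivity analysis for RANO-assessed patients:

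- Derive enhancing-lesion progression as at least a 25% rise from the smallest sum of products on study, baseline included.
- Use the fixed set of measurable enhancing lesions recorded at baseline, because Appendix C otherwise allows the evaluated lesions to change and the nadir would have no defined lesion set.
- Count reappearance of enhancing disease after CR as progression, since a percentage rise from zero is undefined.
- Leave the other RANO criteria unchanged.
- Re-derive confirmed best response, ORR, DOR and PFS together, so that no patient remains in the DOR set on a confirming scan that the new rule calls progression.

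If the database is already locked, report this as post hoc in the clinical study report, where Protocol Section 7 sends deviations from the SAP. No change to Protocol Table 14 or to any treatment rule is proposed.

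The cost is one programmed derivation from lesion data already planned for listing (SAP 3.7.1) and a short SAP addendum. There are four downsides. Durations may be shorter. The threshold is sensitive to small measurement errors. The steroid condition may not be fully verifiable, because medications are recorded only to 30 days after the last dose (SAP 3.5.3). The analysis adds little if sites already used the nadir. These are reasons to keep it as a sensitivity analysis.

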### 6.3. Censoring Rules for PFS

The following censoring rules aim to follow the Food and Drug Administration guidance on Clinical Trial Endpoints for the Approval of Cancer Drugs and Biologics and will be used for PFS analysis.

Situation	Date of Progression or Censoring	Outcome
No post-baseline tumor assessments, in the absence of documented progression or death	Date of first dose	Censored
Documented Progression	Earliest date of progression	Event
No progression, regardless of study discontinuation	Date of last evaluable assessment	Censored
Lost to follow-up without documented progression	Date of last evaluable assessment	Censored
New anticancer treatment started before documented progression	Date of last evaluable assessment prior to new anticancer treatment started	Censored
Death without documented progression and is not after two or more missed tumor assessment visits	Date of death	Event
Death or progression after two or more missed tumor assessment visits	Date of last evaluable assessment	Censored

[source: <https://www.fda.gov/downloads/Drugs/Guidances/ucm071590.pdf>]

Signature Page for VV-CLIN-000865 v1.0

Approval Task Task Verdict: Approved	[REDACTED]	Clinical Development 11-Apr-2024 18:33:51 GMT+0000
---	------------	---

Approval Task Task Verdict: Approved	[REDACTED]	Clinical Development 11-Apr-2024 21:27:16 GMT+0000
---	------------	---

Approval Task Task Verdict: Approved	[REDACTED]	Clinical Development 12-Apr-2024 20:55:52 GMT+0000
---	------------	---

Signature Page for VV-CLIN-000865 v1.0
